

Table 1. Unit guidelines for extubation criteria

WEIGHT (grams)								
	< 1000	1000-2000	2000-3000	> 3000				
MAP	8	9-10	10-12	12				
Amp	16	18	20	22				
FiO ₂	< 0.4							
HFOV								
WEIGHT (grams)								
	< 1000	1000-2000	2000-3000	> 3000				
PIP	< 16	16-20	20					
PEEP	< 6	< 7	< 8					
PS	< 6 – 8							
FiO ₂	< 0.4							
Rate	16 – 20							
PC-SIMV and PC-PSV								
WEIGHT (grams)								
	< 1000	1000-2000	2000-3000	> 3000				
PIP	< 16	16-20	20					
PEEP	< 6	< 7	< 8					
VT	4 – 5 ml/kg							
PS	< 6 – 8							
FiO ₂	< 0.4							
Rate	16 – 20							
SIMV + VG and PSV + VG								

Table 2a. Adjustment of nHFJV support

In order of preference:	
Improving PaO ₂	
 1. Wean FiO₂ until ≤ 0.3 2. Wean PEEP by 1 cm H₂O to a minimum of 6
Improving PaCO ₂	
 1. Wean IMV PIP by 1-2 every 3-4 hours to a minimum of 15 cm H₂O 2. Wean IMV rate by 2 every 3-4 hours to off 3. Wean HFJV PIP by 1-2 every 3-4 hours to minimum of 15 cm H₂O
Worsening PaO ₂ and FiO ₂ > 0.4	
 1. Increase PEEP by 1-2 cm H₂O every 15 minutes to maximum of 12 cm H₂O 2. If no chest rise with IMV breaths, increase IMV PIP by 1-2 cm H₂O to a maximum of 30 cm H₂O
Worsening PaCO ₂	
 1. Increase HFJV PIP by 2-3 cm H₂O until visible chest wiggle to maximum of 30 cm H₂O 2. If no effect, increase HFJV rate by 60 bpm to maximum of 480 bpm 3. If no effect, increase IMV PIP by 1-2 cm H₂O every 30-60 minutes to maximum of 30 cm H₂O 4. If no effect, increase IMV rate by 1-2 bpm to maximum of 20 bpm

Table 2b. Caveats of care with nHFJV support

1) IMV PIP should remain at least 1-2 below the nHFJV PIP so conventional breaths do not interrupt HFJV. Listen to infants' breaths and adjust as needed.
2) If receiving "cannot meet ready conditions" alarm, decrease the IMV breaths until the alarm stops and then increase IMV breaths to goal
3) Set/keep "slope" on Drager IMV breaths to 0.0
4) If increasing stomach gas, can consider weaning nHFJV PIP by 1-2 to minimum of 16 cmH ₂ O
5) Can increase nHFJV PIP by 1-2 if lower levels activate "low PIP" alarm
6) If PAW reaches 12 cm H ₂ O, recommend obtaining chest x-ray
7) Air trapping related to inadequate high frequency expiratory time or excessive nHFJV PIP should not occur due to the non-invasive approach

Table 3. Adjustment of NIPPV support

In order of preference:	
Improving PaO ₂	
 1. Wean FiO₂ until ≤ 0.3 2. Wean PEEP by 1 to a minimum of 5 cm H₂O
Improving PaCO ₂	
 1. Wean PIP by 1-2 every 3-4 hours to a minimum of 15 cm H₂O 2. Wean rate by 5 every 3-4 hours to minimum of 5 bpm
Worsening PaO ₂ and FiO ₂ > 0.4	
 1. Increase PEEP by 1-2 cm H₂O every 15 minutes to maximum of 10 cm H₂O
Worsening PaCO ₂	
 1. Increase PIP by 2-3 cm H₂O to maximum of 30 cm H₂O 2. Increase rate by 5 to maximum of 30 bpm

Figure 1. Silverman Scoring system for respiratory failure

	UPPER CHEST	LOWER CHEST	XIPHOID RETRACT.	NARES DILAT.	EXPIR. GRUNT
GRADE 0	 SYNCHRONIZED	 NO RETRACT.	 NONE	 NONE	 NONE
GRADE 1	 LAG ON INSP.	 JUST VISIBLE	 JUST VISIBLE	 MINIMAL	 STETHOS. ONLY
GRADE 2	 SEE-SAW	 MARKED	 MARKED	 MARKED	 NAKED EAR

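### Does Table 2a's IMV PIP increase for worsening PaO₂ conflict with the pressure gap in Table 2b item 1?

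*Combined protocol and SAP*

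**What the plan says.** Section E.5.a of the combined protocol and SAP gives the initial nHFJV settings, among them HFJV PIP 25 and conventional PIP 24. Section E.8.d.ii refers to Table 2, without distinguishing 2a from 2b, for later adjustments.

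Table 2a lists its steps under the label "In order of preference". The row for worsening PaO₂ with FiO₂ above 0.4 has two steps. The first raises PEEP. The second reads "If no chest rise with IMV breaths, increase IMV PIP by 1-2 cm" H₂O, up to a maximum of 30. The row does not mention HFJV PIP. In the worsening-PaCO₂ row, step 1 is "Increase HFJV PIP by 2-3 cm" H₂O, also capped at 30, and step 3 is "If no effect, increase IMV PIP by 1-2 cm" H₂O. The improving-PaCO₂ row starts with "Wean IMV PIP by 1-2 every 3-4 hours to a minimum of 15 cm" H₂O.

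Table 2b is headed "Caveats of care with nHFJV support". Its item 1 says "IMV PIP should remain at least 1-2 below the nHFJV PIP so conventional breaths do not interrupt HFJV", and then tells staff to listen to the infant's "breaths and adjust as needed". Item 5 allows an HFJV PIP increase of 1-2 in response to a low-PIP alarm.

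**The concern.** The starting pressures are one unit apart, and item 1 asks for a gap of at least 1-2. The worsening-PaO₂ row moves IMV PIP up while saying nothing about HFJV PIP. An infant still on the starting pressures whose oxygenation worsens would therefore either lose the gap or be unable to receive the printed step. The listed HFJV PIP increases have other triggers (worsening PaCO₂ or a low-PIP alarm), so nothing in this row makes room.

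Item 1 gives its purpose as protecting the jet breaths from interruption by conventional ones, and jet ventilation is the mode under test. If staff resolved the clash in different ways, the experimental arm would be delivered less uniformly than the tables suggest.

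**Working it through.** **Inputs.** HFJV PIP 25 and conventional PIP 24 (E.5.a). IMV PIP step +1 or +2 (Table 2a, worsening PaO₂, step 2). HFJV PIP step +2 or +3 (Table 2a, worsening PaCO₂, step 1). IMV PIP wean −1 or −2 (Table 2a, improving PaCO₂, step 1). Minimum gap 1 or 2, the two ways of reading item 1 of Table 2b. The plan states no figure of its own for the gap, so there is none to reproduce.

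**Formulas.** Gap = HFJV PIP − IMV PIP. Room for an IMV PIP increase = HFJV PIP − minimum gap − IMV PIP.

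**One worsening-PaO₂ step 2 from the starting settings.** The starting gap is 25 − 24 = 1. After +1 it is 25 − 25 = 0; after +2 it is 25 − 26 = −1. Both are below the minimum on either reading. The PEEP step that comes before it changes neither set PIP.

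**Room under item 1 in nearby states.**

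| State | HFJV PIP | IMV PIP | Gap | Room, minimum gap 1 | Room, minimum gap 2 |
|---|---|---|---|---|---|
| Starting settings | 25 | 24 | 1 | 0 | none (1 short) |
| After HFJV PIP +2 | 27 | 24 | 3 | 2 | 1 |
| After HFJV PIP +3 | 28 | 24 | 4 | 3 | 2 |
| After IMV PIP wean of 1 | 25 | 23 | 2 | 1 | 0 |
| After IMV PIP wean of 2 | 25 | 22 | 3 | 2 | 1 |

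Apart from the start, only a wean of 1 read against a minimum gap of 2 leaves no room. The starting settings themselves satisfy a minimum of 1 but not of 2, so the plan is consistent with itself at the start only if the smaller figure is the working minimum.

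**Comparison row.** One pass through worsening PaCO₂ (HFJV PIP up, then IMV PIP up) ends with a gap between 27 − 26 = 1 and 28 − 25 = 3, which keeps a minimum of 1. The difficulty is therefore specific to the PaO₂ row at or near the starting pressures.

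**Extremes.** Taking step 2 repeatedly to 30 with HFJV PIP fixed at 25 would give 25 − 30 = −5, but only if Table 2b were ignored throughout. The shared maximum of 30 means IMV PIP could reach at most 29 or 28 under item 1. A maximum is an upper bound, so that is no contradiction. Neither figure adds to the point.

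**Reading the tables together.** The arithmetic shows a breach only if Table 2a is followed without Table 2b. E.8.d.ii points to both. A list of steps followed by caveats is ordinarily a rule with limits on it, and item 1 is phrased as something that should continue to hold. On that reading step 2 is bounded by the current HFJV PIP, and nothing is breached.

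**Link to the analysis.** The specific aims concern reintubation, days of invasive ventilation and BPD. Section 9 compares categorical outcomes by chi-square or Fisher's exact test on an intent-to-treat basis. No set pressure enters the primary comparison.

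**The case for a change.** The strongest reply is that treating item 1 as a limit does not remove the difficulty. Step 2 then has no room at the pressures prescribed for every nHFJV infant at the start, which is hardly a contrived state. PEEP is the only listed step left in the row, and the instruction to adjust names neither a pressure nor a direction. One clinician could raise HFJV PIP and another could withhold step 2, each citing Table 2.

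The missing detail is real, and that part stands. It does not amount to two incompatible instructions. Table 2a does not require HFJV PIP to stay fixed when IMV PIP rises; it is silent. Item 1 attaches bedside discretion to this very gap. The situation also requires several conditions together: worsening PaO₂ with FiO₂ above 0.4, the preferred PEEP step (8 at the start, maximum 12) not being enough, no chest rise with the IMV breaths, and pressures still at or near their starting values. The documents do not say how often these coincide, so no frequency can be given in either direction.

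**Conclusion.** No change to the plan follows. The quoted text and the arithmetic are correct: the starting gap is 1, and one isolated step would make it 0 or −1. Calling that a breach, however, depends on reading Table 2a without its caveats. Read together, the tables leave a small ambiguity that depends on the current settings. At the starting pressures there is no room for worsening-PaO₂ step 2, and the text does not say which pressure is then adjusted. Staff using both tables would see the caveat and its invitation to adjust, so this is a gap that is sensibly filled at the bedside.

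Its reach is the nHFJV arm, planned at 20 of 40 infants, and within it those meeting all the conditions for the step while near the starting pressures. No consequence for safety, bias, the reintubation rate, the sample size or the analysis is shown. E.8.e also has ventilator support recorded at scheduled times. If those records include both PIPs, which is an assumption, the gap actually used can be described afterwards.

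The conclusion rests on taking Table 2b as qualifying Table 2a, as its heading and E.8.d.ii suggest. How E.5.a, worsening-PaO₂ step 2 and item 1 are to be reconciled in wording is a clinical matter for the sponsor's team. I take no position on any setting or on which pressure should move.
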